7.8.2 Laboratory data

The analyses of laboratory data will be descriptive in nature and will be based on BI standards [001-MCG-157] (11).

Laboratory data will be analysed qualitatively via comparison of laboratory data to their reference ranges. Values outside the reference range as well as values defined as possible clinically significant will be flagged in the data listings.

It is the investigator's responsibility to decide whether a lab value is clinically significant abnormal or not (at the RPM/DBLM at the latest).

Descriptive statistics of laboratory data will be calculated by planned time point based on the worst value of the subject at that planned time point (or assigned to that planned time point).

7.8.3 Vital signs

Descriptive statistics over time including change from baseline will be performed for vital signs (BP, PR).

Descriptive statistics will be calculated by planned time point based on the last value of the subject at that planned time point (or assigned to that planned time point).

7.8.4 ECG

Continuous safety ECG monitoring (by investigator)

Clinically relevant abnormal findings will be reported as AEs.

No separate listing or analysis of continuous ECG monitoring will be prepared.

12-lead ECG

Abnormal findings, irrespective of whether they originate from central or local evaluation, will be reported as baseline conditions (at screening) or as AEs (during the trial) if judged clinically relevant by the investigator.

All evaluations of ECG data will be based on the TS, except the exposure-response analyses, which are based on the ECGPCS set.

The following ECG analyses will only be performed:

Listing of individual data

For all quantitative endpoints, listings of individual data will be shown in Appendix 16.2. For QTcB and RR only listings will be provided. Occurrences of notable findings will be flagged.

Comments regarding the ECGs will be listed.

Categorical endpoints

For the categorical endpoints, frequency tables will be provided.

For all subjects with any notable finding in ECG intervals, a separate listing will be created as end-of-text display (based on the same display template as in Appendix 16.2), and the corresponding time profiles will be shown.

Quantitative endpoints

Descriptive statistics (N, mean, SD, min, median, max) will be provided for the changes from baseline over time of QTcF, HR, QT, PR and QRS. The time profiles of mean and SD for the changes from baseline on treatment will be displayed graphically by treatment.

For QTcF and HR changes from baseline, the relationship to the corresponding plasma concentrations will be evaluated using a random coefficient model. For subjects in the ECGPCS, all time points with available ECG endpoints and valid time-matched drug plasma concentrations will be included. For the handling of missing values, see [Section 6.6](#).

The response variable will be the change from baseline in QTcF (Δ QTcF). The placebo subjects will be included in the analysis, setting their plasma concentrations to zero.

As a first step, it is investigated if there is a potential delayed or accelerated (e.g. due to metabolites) effect of the drug on QTcF. A general visual impression will be provided by overlaying time profiles of plasma concentrations and QTcF changes from baseline (Δ QTcF). These figures will be generated for each subject (presented in Statistical Appendix of the CTR), as well as for means per active treatment (presented in the End-of-Text part of the CTR).

The relationship between BI 730460 plasma concentrations and QTcF changes from baseline will be investigated in an exploratory manner using a random coefficient model to estimate the difference in means between BI 730460 and placebo of QTcF change from baseline and its 90% confidence interval at the geometric mean of C_{\max} for each dose. Additionally, the estimated overall slope with its 90% confidence interval will be provided. The used random coefficient model is based on a white paper from Garnett et al. (12) with Δ QTcF as response variable, centered baseline QTc and plasma concentration as continuous covariates, treatment and time as fixed categorical effects, and a random intercept and slope for each subject. For more details refer to [Section 9.3](#).

For visualization, a scatterplot of the BI 730460 plasma concentration against the following individual QTcF values will be provided: For each subject on active treatment and each time point, subtract the mean value of all individual observed Δ QTcF values from the placebo group for this time point from the individual observed Δ QTcF value for this subject and time point. This results in estimates for “individual $\Delta\Delta$ QTcF” values, which should only be used for plotting purposes. The corresponding regression line and its pointwise confidence bands as well as and the geometric mean of C_{\max} for each dose will additionally be displayed in the plot.

To check model assumptions, the conditional residuals will be plotted and presented in the Statistical Appendix of the CTR. In case of non-linearity or if there is evidence for a delayed effect, further models will be explored in order to better characterise the PK-ECG relationship (e.g. effect compartment models, non-linear models, etc.).

All of the above described graphical and statistical analyses will be also performed for HR in place of QTcF.

Appropriateness of heart rate correction methods of QT interval

To evaluate the appropriateness of the heart rate correction methods, the slope of the relationship of QTcF interval versus RR interval (values log-transformed using the natural logarithm) will be estimated by applying the random coefficient model described in [Section 9.1](#) using all time points. A scatterplot of QTcF vs RR including the overall regression line will be included in the Statistical Appendix of the CTR. The resulting (fixed effect) slope together with two-sided 95% confidence intervals will be included in the footnote for this plot.

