## FLOW CHART FOR THE SINGLE RISING DOSE PART

Visit	Day	Planned time (relative to drug administration [h:min])	Approximate clock time of actual day [h:min]	Event and comment	Safety laboratory	PK  blood	12-lead ECG	Continuous ECG monitoring	Vital signs (BP, PR)	Questioning for AEs and concomitant therapy 	
1	-21 to -1			Screening (SCR) 	x		x 		x		
2	-3 to -1	-72:00	08:00	Ambulatory visit	x 					x	
		1	-2:00	06:00	Admission to trial site	x 				x 	
			-1:30	06:30					x 		
			-1:15	06:45					x 		
			-1:00	07:00					x 		
			-0:30	07:30	Allocation to treatment 		x 				
			0:00	08:00	Drug administration					▲	
			0:30	08:30			x		x 		x
			1:00	09:00			x		x 		x
			1:30	09:30			x				
			2:00	10:00	240 mL fluid intake		x		x 		x
			2:30	10:30			x				
			3:00	11:00			x		x 		x
			4:00	12:00	240 mL fluid intake, thereafter lunch 	x	x 		x 	▼	x
			6:00	14:00			x		x 		x
			8:00	16:00	Snack (voluntary) 		x		x 		x
			10:00	18:00	Dinner 		x		x 		
			12:00	20:00			x		x 		x
			2	24:00	08:00	Breakfast (voluntary)  , discharge from trial site	x	x	x 		x
				34:00	18:00	Ambulatory visit		x	x 		x
	3	48:00	08:00	Ambulatory visit		x	x 		x		
	4	72:00	08:00	Ambulatory visit	x	x			x		
	5	96:00	08:00	Ambulatory visit		x			x		
	8	168:00	08:00	Ambulatory visit	x 	x					
4	9 to 13			End of trial (EOT) examination 	x		x 		x	x	

1. Subject must be informed and written informed consent obtained prior to starting any screening procedures. Screening procedures include physical examination, check of vital signs, ECG (including rhythm strip of at least 15 minutes), safety laboratory (including drug screening), demographics (including determination of body height and weight, smoking status and alcohol history), relevant medical history, concomitant therapy and review of inclusion/exclusion criteria. Pharmacogenetic samples will be collected if needed.

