In treatment T (tablet fed) of the BA part, a high-fat, high-calorie meal will be served 30 min before drug administration. The meal must be completely consumed prior to drug administration. The composition of the standardised high-fat, high-calorie meal will be in compliance with the FDA guidance ‘Food-Effect Bioavailability and Fed Bioequivalence Studies’ [[R03-2269](#)] as detailed in Table 4.1.4: 3.

Table 4.1.4: 3 Composition of the high-fat, high-calorie meal

Ingredients	kcal
Sum 	984

 The total caloric content was supplied approximately as following: 150 kcal as protein, 250 kcal as carbohydrate, and 500 to 600 kcal as fat.

Subjects will be kept under close medical surveillance until at least 24 h following drug administration. During the first 4 hours after drug administration subjects of the SRD part will be confined to bed with a bed inclination angle of at least 45 degrees unless lower or supine positioning is required for trial-related measurements (e.g. recording of 12-lead ECG). During the first 4 hours after drug administration subjects of the BA part will only be allowed to lie down if supine positioning is required for trial-related measurements (e.g. recording of 12-lead ECG). For restrictions with regard to diet see Section [4.2.2.2](#).

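### The first-step overlay for a delayed QTcF or heart-rate effect is not placebo-corrected, so meal and time-of-day changes shared with placebo can imitate or hide a delay (minor, cheap to improve)

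*SAP*

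**What the plan says.** SAP 7.8.4 (quantitative endpoints) begins the concentration–QTcF analysis by asking whether the drug effect runs behind or ahead of concentration. The tool is a visual one: "overlaying time profiles of plasma concentrations and QTcF changes from baseline". The figures are made for each subject "as well as for means per active treatment". Neither placebo subtraction nor a mean placebo curve is specified for them.

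Later in the section, after the residual plots, the SAP adds that in case of non-linearity or "if there is evidence for a delayed effect, further models will be explored", with effect-compartment models as one example. It then extends everything to heart rate: "All of the above described graphical and statistical analyses will be also performed for HR in place of QTcF".

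Placebo correction is defined in the same section, but only for the concentration scatterplot. That instruction begins "For each subject on active treatment and each time point, subtract the mean value of all individual observed" changes in the placebo group at that time, and calls the result individual ΔΔQTcF. The planned random coefficient model has categorical time and includes the placebo subjects at concentration zero.

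The schedule matters here. SAP 6.7 sets the ECG baseline at one pre-dose time, -1:30. Protocol 4.1.4 states: "During the first 4 hours after drug administration subjects of the SRD part will be confined to bed". The SRD Flow Chart entry at 4:00 reads "240 mL fluid intake, thereafter lunch", with a snack at 8:00 and dinner at 10:00. ECGs are recorded at 6, 8, 10 and 12 h.

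**The concern.** Change from a single fasted early-morning baseline contains whatever QTcF and heart rate do over the day without drug. In this schedule the main drug-free disturbances, meals and the end of bed rest, come at or after 4 h. Protocol 1.2.5 gives a tmax of about 2 to 3 h for a similar compound. If BI 730460 behaves alike, a drug-free rise after lunch falls on the declining limb of the concentration curve, and an overlay shows that pattern as a lagging response. A drug-free fall at the same times could hide a real lag. The 5 min supine rest before each ECG (Protocol 5.2.4.1) limits posture effects but not meal or clock effects.

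At stake is the quality of the first look at delay: the display may prompt a search for delayed-effect models when the drug acts directly, or discourage one when it does not. The section removes drug-free change in its model and its scatterplot, but not in this display.

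**Working it through.** The plan states no figure for this check, so there is none to reproduce. The size was illustrated by simulation.

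**Inputs from the documents**
- ECG times 0.5, 1, 2, 3, 4, 6, 8, 10, 12, 24, 34 and 48 h (SAP Table 6.7: 1).
- Half-life about 14 h (Protocol 2.3).
- 6 active subjects per dose; pooled placebo 2 × 6 completed groups = 12 planned (SAP 6.1 and 7).

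**Assumed inputs**
- Absorption rate ka = 1.2/h, chosen to put tmax in the 2 to 3 h range.
- Direct, undelayed effect E = 0, 5 or 10 ms at Cmax.
- Drug-free excursion A = 0 to 10 ms, shared by active and placebo. Its relative shape is 0 up to 4 h, then 1 at 6 h, 0.7 at 8 h, 0.5 at 10 h and 0.8 at 12 h.
- SD 5 ms between subjects and 6 ms residual.

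**Step 1, concentration.** ke = ln 2/14 = 0.0495/h. tmax = ln(ka/ke)/(ka − ke) = ln(1.2/0.0495)/1.1505 = 2.77 h. Relative to Cmax, c = 1.00 at 3 h and 0.89 at 6 h.

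**Step 2, without noise.** Uncorrected mean change = E·c(t) + A·shape(t). For E = 5 and A = 3:
- at 3 h: 5 × 1.00 + 0 = 5.0 ms;
- at 6 h: 5 × 0.89 + 3 × 1 = 7.45 ms.

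The uncorrected profile peaks at 6 h. Subtracting the placebo mean leaves 5.0 ms at 3 h and 4.45 ms at 6 h, so the corrected profile peaks at 3 h, the sampled time nearest tmax. The 6 h value overtakes the 3 h value once A exceeds E × (1.00 − 0.89), which is 0.55 ms for E = 5.

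**Step 3, with noise.** A trial counts as looking delayed if its day-1 mean profile peaks at least 3 h after tmax, that is at 6 h or later. Each scenario has 3,000 trials. Entries are uncorrected / placebo-corrected.

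| Drug-free change A | E = 0 | E = 5 ms | E = 10 ms |
|---|---|---|---|
| 0 ms | 45% / 45% | 34% / 37% | 26% / 29% |
| 3 ms | 80% / 45% | 74% / 38% | 64% / 29% |
| 5 ms | 94% / 44% | 90% / 37% | 84% / 29% |
| 8 ms | 99% / 45% | 99% / 37% | 98% / 28% |
| 10 ms | 99.7% / 45% | 99.7% / 37% | 99.5% / 29% |

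Correction brings the share back to about its level with no meal effect. It does not remove the noise of a six-subject mean.

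**Step 4, heart rate.** Two runs assumed a direct effect of 4 to 8 bpm, a drug-free rise of 4 to 8 bpm, SD 4 bpm and tmax 2.5 h. The mean profile peaked at 6 h or later in 90–100% of trials uncorrected against 24–35% corrected in one run, and in 87–100% against 23–35% in the other.

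**Step 5, the planned model.** The fixed part (concentration, treatment, categorical time, placebo included) was fitted by least squares to simulated data with a true slope of 5 per 200 mg Cmax, 300 runs each. Mean slopes were 5.4, 5.2 and 4.9 for A = 0, 5 and 10 ms. The simulation error of each is about 3/√300 = 0.17, and the largest departure from 5 occurs with no excursion, so it is not drift bias. A similar heart-rate check gave 4.0, 4.1 and 3.9 for a true 4 bpm, and 8.1, 8.1 and 7.9 for a true 8 bpm, with drift of 0, 4 and 8 bpm.

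**Step 6, further models.** In that heart-rate check, with the time term and placebo subjects kept, an effect-compartment curve beat the true direct one in 16%, 15% and 14% of runs (true 4 bpm, drift 0, 4 and 8) and in about 1% (true 8 bpm). Shared drift added no false preference for delay.

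**The case against.** The SAP says that the overlay gives a general visual impression. The mention of further models stands in the paragraph on residuals, and those residuals come from a model that already removes shared time effects. Mean change profiles are plotted by treatment elsewhere in the section, and placebo is one of the treatments. The overlay is also drawn for every active dose, including 2 mg, where Protocol 2.1 expects no relevant biological activity; a meal effect would appear there as much as at 200 mg. The criterion of a peak at 6 h or later is not the SAP's, and the excursion sizes and SDs are not in the documents. Section 9.3, to which the SAP refers for model details, is not in the text available, so a criterion for delay may exist there.

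Most of this stands, and it limits severity. A careful reader could compare doses and consult the placebo profiles. It does not remove the point: the text available does not link those profiles to the judgement of delay, and the display named as the first step carries a known confounder that the same section already knows how to remove.

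**Conclusion.** The point holds as a minor one: the uncorrected overlay can suggest a delay that is not there, or hide one that is. Under the assumptions above, with an undelayed 5 ms effect, the excess of apparent delay is roughly 36 to 62 percentage points (74% − 38% to 99.7% − 37%). That size depends on the assumed excursion, SDs, tmax and peak-time rule; the masking direction was not simulated.

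A reader might infer three stronger things, which the documents do not support.
- *That the overlay alone decides between a direct and a delayed model.* The SAP gives it no such role, and residuals are examined as well.
- *That an apparent delay replaces the planned model.* The random coefficient model is not conditional on the overlay, and further models are only to be explored, in an analysis called exploratory.
- *That the estimated effect at Cmax is shifted.* The planned model has categorical time and the placebo subjects, and its slope showed no drift bias in the checks. These checks used a simplified fit without random slopes and assumed that drift is the same on active and placebo.

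**What to change.** In SAP 7.8.4:
- Draw the concentration overlays with placebo-corrected values. For each active subject, use the individual ΔΔQTcF already defined. For each dose, use the active mean change minus the pooled placebo mean at the same planned time, with its 90% CI. Do the same for heart rate.
- State that delay is judged on these plots together with the model residuals.
- State that any further model keeps the time effect and the placebo subjects.

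Uncorrected changes remain visible in the by-treatment time profiles. The SAP reserves individual ΔΔQTcF for plots, and this use respects that.

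The cost is a few sentences and one change of plotted variable, using values already computed for the scatterplot. The downside is that the sampling error of the placebo mean (12 planned subjects) is added to each plotted point. With the assumed residual SD of 6 ms, the residual standard error of a dose mean rises from 6/√6 = 2.4 ms to √(36/6 + 36/12) = 3.0 ms. With no meal effect, this raised the share that looks delayed only from 34% to 37% (5 ms effect).

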7.8.5 Others

Physical examination

Physical examination findings will be reported as relevant medical history/baseline condition (i.e., a condition already existent before intake of study drug) or as AE and will be summarised as such.

No separate listing or analysis of physical examination findings will be prepared.

